8.3.3 Cost and cost-effectiveness study

When all the cost components have been collected, the data will be aggregated or collated in Excel. Once the summary is completed, a cost profile of the programme activities will be derived and after the total costs of the programme have been calculated, the unit costs will then be derived (i.e. total costs divided by the sample size). These profiles are useful in highlighting major cost components (and thus identifying potential areas where improvements in efficiency may have significant impact on costs). For this evaluation, analysis will focus on full costing and incremental costing approach. Total, average and incremental costs per year will be estimated. Costs associated with increasing the oxygen saturation referral threshold will be estimated based on the additional proportion of children meeting referral criteria.

When available, effectiveness data will be combined with the cost data and cost per DALY averted will be estimated. Effectiveness will be modelled using the information on severe outcomes such as mortality, and secondary hospitalization, adjusting as far as possible the level of severity of illness of the child at presentation.

At primary care facilities, these will include measurements (when taken by healthcare providers) such as anthropometry, respiratory rate, temperature and routine investigations where available (e.g. haemoglobin, CRP), and oxygen saturation (post-intervention/in intervention arms). We will also use diagnosis and severity classification recorded by primary care providers.

At hospital level, we will also utilize the same measurement data, and other vital sign data (such as a paediatric early warning score if recorded), decision to admit, intensive care and / or ventilation, provisional and final diagnosis, admission outcome (discharge, death, left against medical advice) and length of hospital stay. We will then use these indicators, along with mortality from phone call follow-up data by Day 28, to predict probability of mortality based on available literature. The DALY calculation will be based primarily on probability of mortality

over a relatively short horizon (to be determined based on a review of literature, likely between three and six months to reflect the time windows used in post hospital discharge mortality studies). The types of illnesses considered do not typically lead to long-term disability, and the duration of illness is too short to have a big impact on DALY calculations. We will not use age weights: we will use GBD (2017) DALYs,⁶⁰ and we will not use country-specific disutility data, both since we are unsure these exist for all the countries, and they render cross-country comparisons more difficult.

Sensitivity analysis

As not all data will be available precisely, we will explore possible assumptions using sensitivity analysis which will assess how the estimates would react to percentages changes in the value of the assumptions. It can help the reviewer to determine which parameters are the key drivers of a model's results. Guidelines and standard textbook recommend that economic evaluations should include sensitivity analysis.⁶¹ We will undertake one-way sensitivity analysis of key parameters using the major outcome and cost parameters. Typically, such analyses are more sensitive to the assumptions about outcomes, and for this we have to rely on the best judgement of the epidemiologists.

9 Monitoring

All studies will be conducted in accordance with the protocol and international and applicable national regulatory requirements. The pragmatic cluster RCT will be monitored in accordance with ICH Good Clinical Practice in addition to the aforementioned requirements. Independent trial monitoring will be conducted by the Clinical Operations Unit within the Department of Medicine at Swiss TPH (separate unit from lead investigators). The Clinical Operations Unit will be responsible for setting up and carrying out the monitoring of trial conduct using a risk-based approach, combining on-site, remote and centralised monitoring.

On-site monitoring will be done for a random selection of sites and can be triggered in addition for sites appearing to be breaching. Screening data, consent, recruitment rates and missing data on primary and important secondary endpoints will be reviewed remotely. Findings of remote monitoring may influence on-site monitoring.

For the pragmatic cluster RCT, an independent data monitoring committee (DMC) will be established, comprising of a Chair, Biostatistician and Clinician with relevant experience. The DMC will meet after three months from the study start to review and evaluate the interim analysis results. In addition, regular reviews will be conducted throughout the course of the study as described and agreed in the DMC charter. The DMC will provide the research steering committee with recommendations after blinded and unblinded reviews of relevant data on trial progress and safety, and any issues identified by monitors.

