3.1 Rationale for pulse oximetry

Hypoxaemia, a reduction in blood oxygenation, has a myriad of causes in children – both respiratory and non-respiratory, but regardless of the cause, is strongly associated with mortality.¹⁵ A meta-analysis of 13 studies on 13,928 children found a 5.5 fold increased risk of death among children with acute lower respiratory infection (ALRI) with oxygen saturation (SpO₂) below 90%.¹⁵ The association of hypoxaemia with mortality in non-respiratory conditions is less extensively documented, but a recent large study in Nigeria found adjusted odds of death in hypoxaemic children to be 7.1 in ALRI, and range from 5.9 to 6.6 in the next most common causes of hypoxaemia (malaria, acute febrile encephalopathy, sepsis, seizures).¹⁶

The prevalence of hypoxaemia is estimated to be around 13% among children with WHO defined suspected pneumonia.¹⁷ Prevalence is also high among sick neonates (18 – 23%), malaria (3 – 17%), meningitis (3 – 15%) and malnutrition (2 – 8%).^{ibid} Studies have further demonstrated the importance of hypoxaemia in children with asthma, sepsis, malaria, sickle cell disease, tetanus and a variety of neonatal illnesses.^{16,18-22} However, the relative contribution of different diseases to the burden of hypoxaemia is highly variable in different settings¹⁷, and likely to reflect the local burden of disease. For example, in the aforementioned study of 23,926 hospitalised children in Nigeria, among all children (28 days – 14 years) with hypoxaemia, 37% had ALRI, 33% malaria, 32% acute febrile encephalopathy, 27% sepsis and 18% seizures. In

countries facing a lower burden of malaria, such as India (2.2% of under 5 deaths are attributed to malaria, compared to 13.2% in Nigeria), whilst systematic data on hypoxaemia burden is not available, this distribution is likely to be different.²³

Given the prevalence of hypoxaemia and its role in mortality, a number of studies have sought to evaluate the predictive power of clinical signs to detect hypoxaemia and guide oxygen therapy. But no single sign or combination of signs has reliably been found to detect hypoxaemia with adequate sensitivity or specificity.²⁴ Using clinical signs alone thus leads to a failure to identify all children who need oxygen and unnecessary administration of oxygen (which is often in scarce supply) for children who do not need it.²⁴

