- Children 2 – 59 months of age with IMCI signs of moderate / severe disease (IMCI 'yellow' or 'red' classification)

These criteria aim to identify children with the highest likelihood of having hypoxaemia whilst avoid unnecessary referrals of children with a low likelihood of having hypoxaemia and a false positive result, as well as avoiding over-burdening healthcare providers or contributing to clinic delays.

Young infants represent a small proportion of all clinic attendees⁴⁶, but with a relatively high prevalence of hypoxaemia and risk of severe disease and mortality.^{1,7,16} Children with cough or difficulty breathing represent around 40 – 70% of children attending primary care. Children with WHO-defined suspected pneumonia (around 15 – 30% of clinic attendees)^{7,46,47} are more likely to be hypoxaemic than those with cough / cold, but respiratory rate, one of the key differentiating signs is often not measured.^{16,47,48} All children with cough / difficulty breathing are therefore chosen to avoid missing children inappropriately classified as not having suspected pneumonia.

Lastly, children presenting with signs of moderate or severe disease are included to ensure detection of children with illnesses such as sepsis, meningitis, malaria, malnutrition, diarrhoea,

anaemia that may also present with hypoxaemia.^{16,17} Children with mild disease – such as diarrhoea with no evidence of dehydration, fever with no evidence of malaria, meningitis / encephalitis, or complicated measles – are very unlikely to have hypoxaemia and pulse oximetry use will therefore not be advised in this group.

In certain circumstances, there may be a deviation from these criteria for operational reasons. Such circumstances will be agreed with local decision-makers, but, for example, may include the use of pulse oximetry during a triage step in large, high volume facilities. In such circumstances, preference may be given to using pulse oximetry on all sick children. In the event that this occurs, children found to have low oxygen saturation will be triaged for immediate assessment by a clinician, who may repeat the pulse oximetry measurement if needed.

In India, the Ministry of Health and Family Welfare opted to recommend be used in the assessment in all sick children under five years of age.

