admission) and admission outcome (final diagnosis, discharge against medical advice, death). The same data will be collected for children who visit a non-hospital higher-level of care (emergency or admission unit of a primary or secondary care facility).

It is expected that some participants may present at the same or another health facility enrolled in the study during the follow-up period. These visits and the findings will be recorded on the appropriate scheduled / unscheduled visit eCRFs.

[figure not shown]

Fig. 5. Flowchart of the pragmatic cluster randomised controlled trial. CDSA = Clinical Decision Support Algorithm. CG = Caregiver. HCP = Healthcare provider. OPD = Out-patient department. Arm 1 not applicable in India.

Tab. 4. Schedule of the visits and associated CRFs for the pragmatic cluster RCT. Arm 1 not applicable in India. The different types of data collectors are represented by the following icons:

 Facility-based research assistants

 Research assistant rotating between different referral health facilities

 Healthcare providers

 Call centre-based research assistant

		Health facility baseline visit			Higher level of care visit ^{1,Err r!} Bookmark not defined.			Scheduled ² or unscheduled visit at any study facility			Phone follow-up		
		Time point / window	Day 0		Day 0-7	Day 1 -28			Day 7	Day 28 [28 - 35]			
		Data collection method	Prospective data collection		Review of medical records / registries	Prospective data collection			Phone interviews	Phone interviews			
		Randomization ³	Arm I	Arm II	Arm III				Arm I	Arm II	Arm III		
Events		Forms											
Informed consent			-										
Screening			TIMCI-01										
Identification & contact information	Full identification		TIMCI-02a										
	Contact information		TIMCI-02b										
	Identification and contact information check		TIMCI-02c										
	Referral facility identification		TIMCI-02d										
	Follow-up identification check		TIMCI-02e										
Socio-demographics			TIMCI-03										
Visit info		Care seeking behaviour, transport and costs for visiting health facility reported by caregiver	TIMCI-04a										

	Visit and admission info recorded by referral facility (medical records, registries) ^{Error! Bookmark not defined.}	TIMCI-04b											
	Patient journey reported by caregiver at follow-up	TIMCI-04c											
Clinical presentation & medical history	Clinical presentation and medical history reported by caregiver at baseline	TIMCI-05a											

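### The cost-per-DALY model uses Day 0 severity variables, including primary-care SpO2, whose recording depends on the trial arm, so the between-arm comparison can be biased in either direction

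*Protocol*

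**What the plan says.** Protocol 8.3.3 models effectiveness from severe outcomes such as death and secondary hospitalisation, "adjusting as far as possible the level of severity of illness of the child at presentation". The primary-care data named for this are measurements where the provider took them (anthropometry, respiratory rate, temperature, some tests), "and oxygen saturation (post-intervention/in intervention arms"), and the provider's diagnosis and severity class. Hospital data are added. All these indicators, with Day 28 deaths from the follow-up calls, are then used "to predict probability of mortality based on available literature". The section continues: "The DALY calculation will be based primarily on probability of mortality" over a short horizon.

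Other places bear on this:

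- Protocol 8.1.1 has SpO2 at study facilities extracted in the intervention arms. Protocol 6.2.1 excludes facilities that already use oximetry routinely in outpatient consultations.
- Protocol 8.1.1 and Tab. 4 (form TIMCI-07c) also collect SpO2 at the referral facility, if available, without restriction by arm.
- Protocol 6.4.4 describes the DALY model in terms of the proportions referred or hospitalised in each arm, with predicted outcomes and with severity predictors for admitted children.
- Protocol 8.3.3 gives no rule for control children without SpO2. Its sensitivity analysis is one-way, on key outcome and cost parameters.

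**The concern.** A severity variable can be used to compare randomised arms only if it is recorded in the same way in each. Here it is not. Primary-care SpO2 is absent from the control arm by design. The other provider-recorded items are also exposed: Protocol 3.2 cites a study in which respiratory rate was checked in only 16% of children with cough or difficulty breathing, and the interventions aim to improve assessment and classification. How often these predictors are recorded is therefore partly an effect of the intervention.

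Two children with the same illness can then receive different severity scores because of their facility's allocation. If the score predicts risk, the intervention arm can appear to have more expected deaths. If the score adjusts for how ill children were on arrival, the intervention arm looks sicker at baseline and is credited with doing better than expected. Section 8.3.3 allows both uses. Cost per DALY averted is a named output meant to inform scale-up, so the model should not rest on inputs that depend on allocation.

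**Working it through.** The documents give no numerical result for the economic model, so there is no figure to reproduce. The check asks how far mean predicted risk could differ between two arms with identical children and no true effect.

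**Inputs**

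- Risk ratio for death at SpO2 below 90%: RR = 5.5. Protocol 3.1 cites a meta-analysis in acute lower respiratory infection that "found a 5.5 fold increased risk of death among children" with low saturation.
- Hypoxaemia among children with suspected pneumonia: 13% (Protocol 3.1).
- Share of attendees with suspected pneumonia: 15–30% (Protocol 6.3: "Children with WHO-defined suspected pneumonia (around 15 – 30% of clinic attendees").
- Assumption: the 13% applies in primary care, and hypoxaemia outside suspected pneumonia is ignored.
- Assumption: every hypoxaemic child in the intervention arm is measured, and the other predictors are equal between arms.

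**Hypoxaemic share of attendees**

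h = 0.13 × 0.15 = 1.95% to 0.13 × 0.30 = 3.9%.

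**Mean predicted risk**

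Let r0 be the predicted risk of a child with normal SpO2, and s the share of hypoxaemic control children whose SpO2 is recorded at hospital.

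- Intervention arm: r0 × [1 + (RR − 1)h] = r0 × (1 + 4.5h)
- Control arm, missing SpO2 read as normal: r0 × (1 + 4.5hs)
- Control arm, calibrated average risk given to unmeasured children: r0 × (1 + 4.5h)

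**Ratio of intervention to control with no true effect**

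| Handling of control SpO2 | h = 1.95% | h = 3.9% |
|---|---|---|
| Missing = normal, s = 0 | 1 + 4.5 × 0.0195 = 1.09 | 1 + 4.5 × 0.039 = 1.18 |
| Missing = normal, s = 0.5 | 1.04 | 1.08 |
| Missing = normal, s = 1 | 1.00 | 1.00 |
| Calibrated average risk | 1.00 | 1.00 |

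Other values, with s = 0 and missing = normal:

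- RR = 3 (assumed): 1.04 to 1.08.
- RR = 7.1 (the adjusted odds quoted in Protocol 3.1 from a Nigerian hospital study, used here as a risk ratio): 1.12 to 1.24.
- h = 0.5% to 1% (assumed, if hypoxaemia is rarer in primary care): 1 + 4.5 × 0.005 = 1.02 to 1 + 4.5 × 0.01 = 1.05, that is, 2–5%.

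**Same child, different arm**

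A hypoxaemic child measured only at primary care is scored 5.5 times the risk of the same child in control if missing means normal. If the control child gets the average risk, the ratio is 5.5/1.088 = 5.1 to 5.5/1.176 = 4.7. Averaging removes the difference between arms but not between children.

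**Direction under adjustment**

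Suppose instead that observed deaths, equal in both arms, are compared with deaths expected from the recorded severity. Under the first row of the table, the intervention arm's observed-to-expected ratio relative to control is 1/1.088 = 0.92 to 1/1.176 = 0.85. An intervention with no effect would seem to lower mortality by 8–15%.

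**The case against.** Several objections have force.

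**SpO2 is not confined to the intervention arms.** A reader might infer that it is. At primary-care level it is recorded only there, but hospital SpO2 is sought in all arms and also feeds the prediction. This narrows the gap without closing it: hospital values are collected only if available and for children who reach a higher level of care, and Protocol 6.4.2 aims to change admission after referral.

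**Bias is not established.** Section 6.4.4 describes arm-level proportions, so a score computed child by child is an inference. Observed severe outcomes and Day 28 deaths already enter the model and dilute any artefact. The prediction model is still to be built from literature. All this stands and limits the point to a risk of bias. It does not remove the instruction in 8.3.3 to use the arm-dependent variables.

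**A larger figure is tempting but unsupported.** A reader might multiply an illustrative true risk ratio of 0.70 by 1.088–1.176, obtain 0.76–0.82, and conclude that deaths averted are understated by 20–41%. That needs missing SpO2 read as normal and no hospital SpO2 in control. The SAP does treat missing SpO2 as normal (6.1.1), but for trial outcomes, not for this model. The calculation also passes a treatment effect through a Day 0 score that would not carry one, and the protocol's 30% concerns severe complications, not deaths.

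**A sensitivity analysis might suffice.** It would show the problem, but the base case would still depend on variables affected by allocation.

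**Conclusion.** The point holds as a risk of bias in cost per DALY averted whose direction and size depend on choices that 8.3.3 leaves open. It works against the intervention if the variables predict risk and missing SpO2 counts as normal, and in its favour if they adjust for baseline severity.

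For prediction, inflation of mean predicted risk in the intervention arm ranges from none, with a calibrated average risk in control, to about 9–18%. The upper range assumes missing SpO2 read as normal, no hospital SpO2 in control, 13% hypoxaemia among the 15–30% of attendees with suspected pneumonia, and a risk ratio of 5.5. With hypoxaemia assumed at 0.5–1% of attendees it is about 2–5%. Hospital SpO2 and observed Day 28 deaths reduce it further. Only SpO2 has been quantified; the other provider-recorded variables raise the same issue, but the documents give no basis for sizing it.

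A reader should not infer that the DALY results are necessarily biased, or that the trial's two primary outcomes are affected. SpO2 is not part of the definition of either outcome.

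**What to change.** In Protocol 8.3.3 and the health-economic analysis plan:

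- Make the randomised comparison of deaths and severe complications by Day 28 the base-case effectiveness input. Section 8.3.3 already draws on these outcomes; it should say that they carry the between-arm effect.
- Restrict any between-arm severity adjustment or mortality prediction from Day 0 data to variables collected the same way in all arms: age, sex, and caregiver-reported items on TIMCI-03 and TIMCI-05a ("Clinical presentation and medical history reported by caregiver at baseline"). Note that critical or emergency cases may give these after the consultation (Protocol 6.5.1).
- Report the model with primary-care SpO2 and other provider-recorded Day 0 variables as a sensitivity analysis, with a written rule for missing SpO2 in control.
- Keep primary-care SpO2 for costing alternative referral thresholds within the intervention arms, where the asymmetry does not arise.

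This is a change of wording and needs no new data. The cost is a less discriminating risk model and wider uncertainty around cost per DALY.

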9.1 Harms

We will collect data on death and secondary hospitalisations as part of the primary outcome. Given the low-risk nature of the intervention, the pragmatic nature of the trial, and that deaths and hospitalisations are, unfortunately, expected in this population, the DMC will review summarised rates of adverse events will be summarized by intervention and control arms and included in a report for the DMC to review. If a considerable difference (of >30%) is found, we will conduct a more in-depth evaluation (through analysis of clinical data, and collection of additional case note data from hospitals if required) of whether deaths or secondary hospitalisations are attributable to the intervention will be conducted.

9.2 Auditing

Internal or external auditing will be triggered in case of concerns about trial conduct.

10 Ethics and dissemination

10.1 Research ethics approval

Following two independent scientific merit reviews, the protocol will be submitted to all relevant research ethics committees / institutional review boards in each country. Receipts of submission to each local ethical review board will be submitted with the master protocols to the WHO Research Ethics Review Committee (ERC).

For India, this includes a) the National Health Ministry, Uttar Pradesh (NHM-UP), b) the Institutional Ethics Committee (IEC) of KGMU and c) the Health Ministry's Screening Committee (HMSC) of the Indian Council of Medical Research (ICMR)

For Tanzania, this includes a) the National Health Research Ethics Committee (NIMR), b) the Ifakara Health Institute IRB (IHI-IRB) (c) the Medical Research Coordinating Committee (MRCC), and (d) Commission of Science and Technology (COSTECH).

Regulatory status of the intervention

Pulse oximetry

The pulse oximetry device selected for the TIMCI project is the Acare AH-MX device. This was selected as it is available through the UNICEF catalogue, which infers a level of quality and device appropriateness. The competitive procurement process established by UNICEF incorporates pulse oximetry specifications developed through a collaborative process involving global and national level experts. Devices in the catalogue have regulatory approval from a stringent regulatory authority (SRA) such as the United States Food and Drug Administration (US FDA) or Conformité Européenne (CE) mark.

Country level regulatory approval will vary. It is possible that the devices will have approval in some of the countries. If the device does not have pre-existing regulatory approval in a project country, the project team will work with the MOH to receive a waiver to use the device for the study purposes. If appropriate, the study team will continue to work with the manufacturer and MOH in each country to receive a permanent regulatory approval to facilitate scale of that device.

Clinical Decision Support Algorithm

The regulatory classification of clinical decision support software is currently subject to debate at the US FDA, depending on how and in what context the software is used. In this study, the CDSA is intended to provide decision support for the diagnosis and treatment of childhood illness. It will collate and analyse patient-specific information to suggest possible diagnoses and recommend treatment plans or diagnostic tests to healthcare providers (HCPs). These suggestions and recommendations will be evidence-based and will support the decision-making of the HCP when considering treatment options or diagnostic tests for a patient. The HCP may then use this information to make a decision about the care of the patient, along with

other information and factors of which he/she is aware. In addition, the CDSA presents a low risk profile since it will support the implementation of and strengthen the adherence to standard clinical guidelines. These functions do not meet the definition of a medical device per country regulatory authorities and the CDSA is therefore regarded as a non-regulated device.

